## 6. Exhaled nitric oxide

The fraction of exhaled nitric oxide (FeNO) will be measured at each visit according to the

ATS/ERS criteria  using Ecomedics chemiluminescent detector unit (CLD 88sp FENO, Ecomedics, Switzerland), and reported in parts per billion (ppb). Ecomedics measures FeNO from the exhaled breath, which can be used as a marker of eosinophilic airway inflammation. Participants will be instructed to empty their breath away from the mouthpiece, take a normal size breath in through the mouthpiece, and exhale in one single breath at a constant and steady rate. The average of three technically acceptable attempts will be calculated. FeNO is always to be measured prior to spirometry as forced breathing manoeuvres may alter FeNO results.

#### 7. Spirometry, saline challenge and combined sputum induction

Asthma medications are to be withheld (short acting  $\beta$ 2-agonists and anti-cholinergics for 6 hours, long-acting  $\beta$ 2-agonists, combination inhalers and long acting theophyllines for 24 hours, and short acting theophyllines for 12 hours) prior to measuring dynamic lung function using a MedGraphics spirometer (CPFS/D and BreezeSuite software, MedGraphics, Minnesota, USA). Predicted values for forced expiratory volume in one second (FEV1) and forced vital capacity (FVC) will be calculated using *National Health and Nutrition Examination Survey* (NHANES) III data , which accounts for age, gender, race and height. Prior to conducting the assessment, the room temperature, barometric pressure and humidity is to be recorded, and the spirometer calibrated.

Participants will perform the manoeuvre seated in a chair and wearing a disposable nose clip. A new disposable mouthpiece will be attached to the spirometer, and after completing 1-2 tidal breaths, the participant is instructed to inhale to total lung capacity, then forcefully exhale to residual volume. This step is repeated until three reproducible (within 150ml) and technically acceptable results are obtained, with a maximum of eight attempts performed.

Sputum induction coupled with bronchial provocation challenge (to assess airway hyper responsiveness (AHR)) will also be performed at each visit over a standardised 15.5 minutes nebulisation protocol (30s, 1min, 2mins, 4mins, 4mins, 4mins). To determine AHR, the participant is exposed to a mist of hypertonic (4.5%) saline created by a nebulizer (ULTRA-NEB™ ultrasonic nebulizer, DeVilbiss, Model 2000) . This test will commence immediately after spirometry is performed. The participant is instructed to inhale the saline aerosol through the mouthpiece for incremental time periods in doubling doses, for no longer than 15.5 mins. FEV1 is measured after each period of saline inhalation and compared to the baseline value. If the participant's FEV1 falls  $\geq$ 15% below their initial baseline value, the challenge is complete, as this is indicative of AHR. Participants with AHR are administered 400mcg salbutamol via a spacer, and their lung function assessed after 15mins.

During the challenge participants will be encouraged to cough and clear their throat after each period of saline inhalation. This will help to dislodge sputum from their chest wall. The participant is instructed to empty the contents of their mouth into a specimen jar. Sputum

induction will continue until either the completion of 15.5 minutes of inhalation, If the participants FEV1 falls  $\geq 15\%$  again during the test, or if the participant declines to continue.

## 8. Faecal sample collection

Faeces samples will be collected by participants at home using the faeces collection kit (stool collection potty, sterile specimen jar, gloves, specimen bag) provided and stored in the home freezer at  $-20^{\circ}\text{C}$  until the next clinic visit. Samples will be brought into the clinic using the esky with ice brick provided, then stored at  $-80^{\circ}\text{C}$ .

## 6.6 Laboratory methods

### 6.6.1 Induced Sputum samples

#### (a) Processing

Sputum collected by induction during hypertonic saline challenge will be processed within 30 minutes of collection. Mucus plugs will be dispersed using 0.1% dithiothreitol, then total cell counts (TCC) and cell viability (using trypan blue exclusion) will be performed. Cytospins will be prepared and stained (May-Grunwald Giemsa) for differential cell counts, on 400 non-squamous cells as previously described. Using standard morphological criteria, cells will be classified as neutrophils, eosinophil, columnar epithelial, squamous epithelial, macrophages and lymphocytes.

#### (b) Phenotyping

Sputum cell counts of neutrophils and eosinophils will be used to classify subjects by asthma inflammatory phenotype. This is done by converting the cell counts to a percentage of total cells in the sample. The following classifications are used: Eosinophilic asthma: Sputum eosinophils  $\geq 3.0\%$ , Neutrophilic asthma: Sputum neutrophils  $>61\%$ , Paucigranulocytic asthma: Sputum eosinophils  $<3.0\%$  and sputum neutrophils  $<61\%$ , Mixed granulocytic asthma: Sputum eosinophils  $\geq 3.0\%$  and sputum neutrophils  $\geq 61\%$ .

#### (c) Molecular testing

100 $\mu\text{L}$  of sputum plugs will be selected and homogenised in buffer RLT (Qiagen, Hilden, Germany), then stored at  $-80^{\circ}\text{C}$  for RNA extraction and gene expression analysis.

### 6.6.2 Blood samples

#### (a) Processing

Blood will be collected into EDTA tubes, centrifuged at  $20^{\circ}\text{C}$ , 3000 rpm for 10 minutes then plasma will be selected and stored at  $-80^{\circ}\text{C}$ . Remaining blood cells will be used for isolation of PBMCs using the Ficoll-Paque PLUS (GE healthcare, Sydney, Australia) density gradient method, as per the manufacturer's recommendations. Cell counts and viability tests with trypan blue staining were performed. Isolated PBMCs will be stored in buffer RLT for RNA

extraction and gene expression analysis. Nuclear proteins will be extracted from PBMCs using the Active Motif Nuclear Extract Kit (Active Motif, Carlsbad, CA, USA) and quantified by the Bio-Rad protein assay (Bio-Rad, Hercules, CA, USA), as per the manufacturers protocol.

(b) Plasma SCFA

SCFAs will be measured in plasma by gas chromatography (GC). Plasma samples (200  $\mu$ L), containing heptanoic acid (internal standard, 100 nmol) will be extracted with ether (3 mL). The ether layer will be transferred to a clean tube containing 0.2 M sodium hydroxide (50  $\mu$ L). The ether is then removed and the aqueous solution washed again with ether (3ml). The aqueous solution is then transferred to a GC vial and acidified by addition of 1 M phosphoric acid (30  $\mu$ L). The mixture is injected onto a GC column (Zebron FFAP 30 m x 530  $\mu$ m x 1.0  $\mu$ m) and SCFAs (acetate, propionate and butyrate) are quantified against calibration mixtures extracted in the same way.

(c) Total HDAC enzyme activity assay

Total HDAC enzyme activity will be measured in PBMC nuclear protein extracts using the Active Motif fluorescent HDAC Assay Kit (Active Motif, Carlsbad, CA, USA) according to the manufacturer's recommendations. Briefly, the substrate is incubated with 3 $\mu$ g of total nuclear protein extracts and incubated for 60mins. Following incubation, developer solution is added and fluorescence measured at 360nm excitation and 460nm emission (FLUOstar Optima, BMG Labtech, Durham, NC). All samples and standards will be measured in duplicate. A deacetylated HDAC standard curve will be used to quantify HDAC activity ( $\mu$ M/ $\mu$ g).

(d) Total HAT enzyme activity assay

Measurement of total HAT enzyme activity in PBMC nuclear protein extracts will be performed using the Active Motif fluorescent HAT Assay Kit (Active Motif, Carlsbad, CA, USA) according to the manufacturer's recommendations. Briefly, 0.5 $\mu$ g of total nuclear protein extracts is incubated with acetyl-CoA and histone H3 substrate peptide for 20min. Developer solution is then added to react with the free sulfhydryl groups on the CoA-SH, producing a fluorescent reading of acetyltransferase activity. Fluorescence will be measured at 360 nm excitation and 460 nm emission (FLUOstar Optima, BMG Labtech, Durham, NC, USA). All samples and standards are to be measured in duplicate. A standard curve of  $\beta$ -mercaptoethanol will be used to quantify HAT activity ( $\mu$ M/ $\mu$ g).

(e) HDAC subtype protein assays

To determine protein levels of select HDAC subtypes (HDAC2 and HDAC7) in nuclear protein extracts, EpiQuik colorimetric assay kits (Epigentek) will be used as per the manufacturer's instructions. These colorimetric assays work as an ELISA-like reaction, and utilise similar principles and procedures. HDAC2/7 proteins present in the experimental nuclear protein

bind to the unique HDAC affinity substrate that is stably coated on the strip wells. The bound HDAC2/7 is then recognised with a high-affinity HDAC2/7-specific antibody, and the amount of HDAC2/7 is colorimetrically quantified through an ELISA-like reaction following the addition of a secondary detection antibody. The amount of HDAC2/7 is proportional to the intensity of the colour development.

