## 6.4 *Outcome Measures*

Primary: Plasma SCFA

Secondary: Airway inflammation (sputum cell counts, IL-8, FeNO), systemic inflammation (plasma CRP and TNF $\alpha$ ), faecal SCFA and microbiota, lung function, asthma control, molecular mechanisms.

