#### (b) Faecal SCFA

Faecal SCFA concentrations will be determined at Flinders Analytical (Flinders University, Australia) by flame ionisation detection on an Agilent Technologies 7890A gas chromatograph fitted with a flame-ionisation detector using nitrogen as the carrier gas . Approximately 200 µl of unbuffered distilled water is added to 100 mg of faecal sample. Supernatant is collected after centrifugation at 13,000 x g for 10 mins. A 500 µl aliquot of the faecal supernatant is acidified to below pH 2.0 with 85% orthophosphoric acid, and 11 mM 4-methylvalerate was used as internal standard. Samples (1 µl) are separated on a SCE Analytical BP21 column (15 m x 0.25 mm I.D., with a 0.25 µm film thickness). Acetate, propionate, n-butyrate, iso-butyrate, n-valerate and iso-valerate will be quantified using a standard curve with 4-methyl valerate as an internal standard.

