### 6.7 *Sample size calculation*

Based on previous studies , we hypothesise that we would observe a change in plasma acetate of  $\sim 1$ SD. With  $n=15$  subjects, we would have 90% power to detect a difference between groups, using  $\alpha=0.025$  (to avoid type 1 error when comparing 3 groups).

Allowing for 10% dropouts, we aim to recruit n=17 subjects.

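### The written plasma SCFA method (primary outcome) extracts plasma with ether before any acid is added, so nearly all acetate would stay in the plasma and the rest would vary with sample pH

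*Protocol*

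**What the plan says.** Protocol section 6.4 names one primary outcome: "Primary: Plasma SCFA". Section 6.7 rests the sample size on one of these acids: "we hypothesise that we would observe a change in plasma acetate of" about 1 SD, with n=15, 90% power and alpha 0.025.

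Section 6.6.2 describes the assay. For the matrix, "Blood will be collected into EDTA tubes". Part (b) then gives these steps with volumes and concentrations:

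1. 200 µL of plasma, "containing heptanoic acid (internal standard, 100 nmol) will be extracted with ether (3 mL").
2. The ether layer goes into 50 µL of 0.2 M sodium hydroxide.
3. The ether is removed and the aqueous phase is washed with a further 3 mL of ether.
4. "The aqueous solution is then transferred to a GC vial and acidified by addition of 1 M phosphoric acid" (30 µL).
5. Acetate, propionate and butyrate are read against calibration mixtures that go through the same extraction.

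Step 4 is the only acid in the sequence. No pH adjustment of the plasma before step 1 is described there or elsewhere in the protocol. The matrix and pH of the calibration mixtures are not stated.

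**The concern.** Step 2 works because ionised short chain fatty acids leave ether for an alkaline water phase. By the same principle, acids that are already ionised in plasma near pH 7.4 will hardly enter the ether in step 1. The acid in step 4 reaches only the extract and cannot recover what was left in the plasma.

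Low recovery alone would matter less if it were the same for every sample. Near neutral pH, however, the un-ionised share of acetate changes by a factor of about ten per pH unit, so measured acetate would partly reflect the pH of each stored sample. That scatter has nothing to do with treatment. It would fall on the only primary outcome, and on the acid that sets the sample size, in a trial of 17 people.

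**Working it through.** **Inputs from the protocol.** Plasma 200 µL; ether 3 mL; phase ratio r = 3/0.2 = 15; heptanoic acid 100 nmol; n=15, effect 1 SD, alpha 0.025.

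**Assumptions, not in the protocol.** Acetic acid pKa 4.76 (4.6-4.9). Plasma pH 7.4 (7.0-8.0). Ether/water partition K of un-ionised acetic acid 0.5 (0.3-2). Heptanoic acid pKa 4.85, with partition 50-300 for the power figures and up to 500 as a check. Within-person CV of acetate 25%. Sample-to-sample pH SD 0.02, 0.05 or 0.1.

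**The protocol's own figure.** It states no recovery or pH, so only the power can be reproduced. A paired t-test with n=15, effect 1 SD and two-sided alpha 0.025 gives 0.898, in agreement with the stated 90%.

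**Ionisation.** Un-ionised fraction F = 1/(1 + 10^(pH − pKa)). At pH 7.4, F = 1/(1 + 10^2.64) = 0.23%, so 99.77% is ionised. Over pH 7.0-8.0 and pKa 4.6-4.9 the ionised share stays above 99.2%.

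**Recovery in the ether.** R = rKF/(1 + rKF). At pH 7.4 with K = 0.5, rKF = 15 × 0.5 × 0.0023 = 0.017, so R is about 1.7%.

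| pH | R, K = 0.3 | R, K = 0.5 | R, K = 2 |
|---|---|---|---|
| 2.0 | 82% | 88% | 97% |
| 7.0 | 2.5% | 4.1% | 14.7% |
| 7.4 | 1.0% | 1.7% | 6.4% |
| 8.0 | 0.3% | 0.4% | 1.7% |

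At pH 7.4, therefore, 93.6-99.0% of acetate stays in the plasma.

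**Does another reagent acidify the plasma?** The internal standard gives 100 nmol/200 µL = 0.5 mM. At an assumed buffer capacity of 10-40 mM per pH unit, that lowers pH by only about 0.01-0.05. In the vial, 30 µL × 1 M = 30 µmol of acid meets 50 µL × 0.2 M = 10 µmol of base. The final acidification is sufficient, and the gap is only at the first step.

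**What the internal standard corrects.** The same formula gives heptanoic acid recovery at pH 7.4 of 68% (partition 50), 93% (300) and 95% (500). The log of the acetate/standard ratio moves per pH unit by about 2.303 × 0.998 × (R of heptanoic acid − R of acetate):

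- partition 50: 2.303 × 0.998 × (0.678 − 0.017) = 1.52, and exp(0.152) − 1 = 16% per 0.1 pH;
- partition 300: 2.303 × 0.998 × (0.927 − 0.017) = 2.09, and exp(0.209) − 1 = 23% per 0.1 pH.

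With no correction the figure would be exp(0.230) − 1 = 26%. The standard therefore helps only in part.

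**Power.** Added CV = slope × SD(pH), taken as independent between samples. Diluted effect d = 1/√(1 + (added CV/0.25)²), put into the same paired t-test.

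| SD(pH) | Added CV | d | Power |
|---|---|---|---|
| 0.02 | 3.0-4.2% | 0.99 | 0.89 |
| 0.05 | 7.6-10.4% | 0.96-0.92 | 0.87-0.84 |
| 0.10 | 15.2-20.9% | 0.86-0.77 | 0.78-0.68 |

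**The case against.** The strongest reply is that the protocol does not mention acid, which is different from saying that there is none. Back-extraction into sodium hydroxide makes sense only if free acids are already in the ether, so a sentence may simply have been left out. A laboratory that recovered about 2% of its acetate would probably notice when calibrating. This is plausible. A reader might infer that the samples will in fact be extracted at neutral pH, and the document does not establish that. But the method lists every other reagent in order with its amount, no other section supplies the step, and the written method needs correcting either way.

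Second, calibrators go through the same extraction, and a constant proportional bias would leave a within-person comparison unchanged. That stands for average recovery if calibrators and plasma share the same pH, which is not stated. It does not remove pH differences between samples. A reader might infer that plasma acetate will be grossly understated; that depends on how the calibrators are made up, and the protocol does not say.

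Third, a reader might infer a definite loss of power. The documents give no pH scatter, and at SD 0.02 the loss almost vanishes.

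Two further inferences fail. The faecal method, where the "faecal supernatant is acidified to below pH 2.0 with 85% orthophosphoric acid", may look like a precedent or a contradiction. It describes no ether extraction, and its acid step is the counterpart of the final vial acidification for plasma. The HAT assay's instruction, "All samples and standards are to be measured in duplicate", may suggest that plasma SCFA is wrongly run once. Section 6.6.2(b) gives no replicate number, and the faecal SCFA and HDAC2/7 protein assays state no duplicates either.

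**Conclusion.** The plasma SCFA method is wrong as written. Over 99% of acetate is ionised at every plasma pH and pKa tried, and about 94-99% would stay in the plasma at pH 7.4, against 3-18% at pH 2. That conclusion does not hinge on any single assumed value. The recovered remainder would vary by roughly 15-25% per 0.1 pH unit after internal-standard correction.

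The consequence for the trial is less certain. Power would be between about 0.89 and 0.68 across the assumed pH scatter of 0.02 to 0.1, at an assumed within-person CV of 25%. The sample size calculation itself reproduces and is not in question. The defect lies in the description of the primary assay; whether it also lies in bench practice cannot be told from the protocol.

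**What to change.** In section 6.6.2(b), before the ether extraction, add one sentence: plasma samples and calibration mixtures, with the internal standard already added, are acidified to a stated pH well below 4.8, naming the acid and the amount. At about pH 2, calculated acetate recovery is 82-97% and hardly depends on small pH differences. If the laboratory already acidifies at this point, correct the written method to say so.

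The cost is one sentence and a few microlitres of acid for each of at most 17 × 6 = 102 plasma samples, plus the calibrators. Design, visits and sample size do not change.

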### 6.6.3 Faecal samples

#### (a) Collection and Processing

Frozen stool samples will be obtained from participants at each clinic visit and stored at -20°C until shipped on dry-ice for offsite analysis.

#### (b) Faecal SCFA

Faecal SCFA concentrations will be determined at Flinders Analytical (Flinders University, Australia) by flame ionisation detection on an Agilent Technologies 7890A gas chromatograph fitted with a flame-ionisation detector using nitrogen as the carrier gas . Approximately 200 µl of unbuffered distilled water is added to 100 mg of faecal sample. Supernatant is collected after centrifugation at 13,000 x g for 10 mins. A 500 µl aliquot of the faecal supernatant is acidified to below pH 2.0 with 85% orthophosphoric acid, and 11 mM 4-methylvalerate was used as internal standard. Samples (1 µl) are separated on a SCE Analytical BP21 column (15 m x 0.25 mm I.D., with a 0.25 µm film thickness). Acetate, propionate, n-butyrate, iso-butyrate, n-valerate and iso-valerate will be quantified using a standard curve with 4-methyl valerate as an internal standard.

#### (c) Faecal microbiota

Extraction and quantification of bacterial DNA from faecal samples, and sequencing of the V4 hypervariable region of the bacterial 16S rRNA gene, will be performed as described previously . Quantitative PCR assays will be used to assess levels of bacterial species as described previously . Levels are normalised to total bacterial load, and differences resulting from treatment expressed as fold change . Faith's phylogenetic diversity is calculated using QIIME (version 1.8.0, [Caporaso, 2010]) and taxa richness, Shannon-Weiner diversity, and Simpson's evenness calculated using PRIMER (version 6, PRIMER-E Ltd, Plymouth, UK). Bray Curtis similarity is calculated using the beta\_diversity.py QIIME script. Principal coordinate analysis will be used to visualize sample clustering based on Bray Curtis similarity distances. Distance from centroid is calculated using PRIMER. Permutational multivariate analysis of variance (PERMANOVA) was used to test the null hypothesis of no difference amongst a priori-defined groups using PERMANOVA + add-on package for PRIMER, computed using unrestricted permutation of raw data with 9,999 random permutations at a significance level of 0.01. Level of microbiota change resulting from treatment will be assessed based on Bray Curtis similarity distance between paired pre-

treatment and post-treatment samples.

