#### Randomisation

All participants will receive both treatments and the placebo. Treatment order will be randomly allocated via unique randomisation codes using a 3x3 latin square method  by an

independent statistician. The randomisation service will be managed by an independent statistician at the Hunter Medical Research Institute.

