## Study Visits

Participants will be screened for study eligibility by telephone prior to study commencement, and will then attend a screening visit where they will have a brief medical examination, dietary questionnaire, have their blood pressure, weight and height measured. If no abnormalities or exclusion criteria are identified, they will be entered into the study. They will commence the study background diet for 2 weeks, then attend the HMRI clinic on 6 occasions, before and after each 7 day intervention (inulin, inulin+probiotic and placebo), which will be separated by 2 weeks (Figure 4). During each intervention phase, participants will be telephoned for motivational purposes, to record compliance with the intervention, the study diet, and to establish whether any adverse effects have been experienced.

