### 6.6 *Statistical Analysis*

Analysis will be performed with STATA 15 (StataCorp, College Station, Texas, USA) and reported as mean  $\pm$  standard deviation or median [interquartile range]. Within group comparisons of outcomes compared to baseline will be assessed using the student t-test or Wilcoxon signed-rank tests. Per protocol analysis of mean difference in outcomes between treatments will be tested using mixed model regression, accounting for repeated measures. An independent ANOVA of period totals by treatment sequence will be used to test the assumption of no carry over effects. Associations will be assessed using Spearman's correlations. Significance will be accepted if  $p < 0.05$ .

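### The PERMANOVA on faecal microbiota is specified with unrestricted permutation and no participant term, so as written it ignores the crossover pairing and loses power for small to moderate treatment shifts

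*Protocol*

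**What the plan says.** Protocol section 6.6.3 (c), Faecal microbiota, uses PERMANOVA "to test the null hypothesis of no difference amongst a priori-defined groups", with the test "computed using unrestricted permutation of raw data with 9,999 random permutations at a significance level of 0.01". It lists no factors, and names neither a participant or period term nor a restriction on the permutations.

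The samples are repeated within person:

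- Randomisation (section 6.1): "All participants will receive both treatments and the placebo".
- Study Visits (section 6.3): participants "then attend the HMRI clinic on 6 occasions, before and after each 7 day intervention".
- Section 6.6.3 (a): "Frozen stool samples will be obtained from participants at each clinic visit".

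Two other statements bear on the point. Section 6.6.3 (c) ends with a separate within-person measure, the Bray Curtis distance between each person's samples before and after a treatment. Section 6.6, Statistical Analysis, says that mean differences between treatments "will be tested using mixed model regression, accounting for repeated measures".

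**The concern.** With no treatment effect, and setting period effects aside, samples from one person can be swapped with each other. Samples from different people cannot, because each person has a characteristic community. Shuffling labels over all samples treats them as independent. The reference distribution then contains the differences between people, whereas the treatment contrast in a crossover is made within people.

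Faecal microbiota is a named secondary outcome, and the hypothesis in section 3 expects its composition to improve. If the test runs as a plain group comparison, a non-significant result could mean that composition did not shift, or only that the test ignored the pairing.

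**Working it through.** **Plan's own figure.** The protocol gives no power for the microbiota. Its only power statement (section 6.7) is for plasma acetate: 90% with 15 people, a change of about 1 SD and alpha 0.025. A paired t test with n = 15, d = 1 and two-sided alpha 0.025 gives 89.8%, and 15 / 0.9 = 16.7, rounded up to 17. Both reproduce, as a within-person comparison.

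**Counts.** Six samples per person give 15 × 6 = 90 or 17 × 6 = 102 samples. The smallest p-value is 1 / 10,000 = 0.0001, so the number of permutations is not the problem.

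**Why the test is conservative.** Take 15 people with three post-treatment samples each (N = 45), between-person variance B, within-person variance W and no treatment effect. The following holds for one variable and carries over approximately to sums of squares on distances.

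- Treatment mean square (2 df): expectation W, because person effects cancel in a balanced crossover.
- One-way residual mean square (42 df): [14(W + 3B) + 28W] / 42 = W + B.
- The observed ratio therefore centres near W / (W + B) = 1 − share, where share = B / (W + B).
- Under unrestricted shuffling both mean squares have the same expectation, so the reference ratio centres near 1.

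At shares of 0.23, 0.44, 0.69 and 0.83 the observed ratio centres near 0.77, 0.56, 0.31 and 0.17 and is compared with a distribution centred near 1. With a participant term the residual (28 df) has expectation W, and the mismatch goes.

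**Simulation A.** Log-normal communities of 40 taxa, a shift in 4 taxa in both active arms, Bray Curtis distance, 15 people, three post-treatment samples, alpha 0.01. The share and the shift are assumptions. The rows below used 250 data sets and 399 permutations each; the simulation standard error is about √(0.5 × 0.5 / 250) = 0.03 at a power of 0.5.

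| Share (approx.) | Shift (log units) | One-way, unrestricted | Participant term, unrestricted | Within-participant permutation |
|---|---|---|---|---|
| 0.23 | 1.0 | 0.036 | 0.148 | 0.148 |
| 0.44 | 1.0 | 0.012 | 0.204 | 0.196 |
| 0.68 | 1.0 | 0.000 | 0.436 | 0.468 |
| 0.82 | 1.0 | 0.000 | 0.608 | 0.672 |
| 0.23 | 2.0 | 0.692 | 0.860 | 0.872 |
| 0.42 | 2.0 | 0.584 | 0.912 | 0.908 |
| 0.66 | 2.0 | 0.508 | 0.976 | 0.984 |
| 0.79 | 2.0 | 0.364 | 0.992 | 0.992 |
| 0.21 | 2.5 | 0.872 | 0.928 | 0.928 |
| 0.76 | 2.5 | 0.716 | 1.000 | 1.000 |

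With no effect, the one-way test rejected in 0.015 of data sets at share 0, in 0 to 0.003 at about 0.23, and in none from 0.44 upward. The two versions that use the participant rejected in 0.000 to 0.020, in line with the nominal 0.01. Results with 17 people or six samples per person were similar.

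**Simulation B.** A separate run with 15 people, three post-treatment samples, alpha 0.01 and assumed shares of 0.3 to 0.7. A given shift was easier to detect than in A, so compare columns and not absolute levels across the two.

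| Shift (log units) | One-way, unrestricted | Pairing used |
|---|---|---|
| 1.0 | 0.01–0.11 | 0.55–0.91 |
| 1.5 | 0.36–0.69 | 0.93–1.00 |
| 2.0 | 0.97–0.99 | 1.00 |

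Unrestricted permutation with a participant term gave 0.53 to 0.87 at 1.0 log unit. Both runs agree on direction and cause: the loss is large for small to moderate shifts, shrinks as the shift grows, and comes mainly from leaving the participant out.

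**The case against.** The strongest reply is that the protocol never writes out a model. It speaks of pre-defined groups without saying that they are treatments, and model terms for a laboratory outcome are often left to an analysis plan, which is not shown here. Unrestricted permutation is also workable once a participant term is present. Both points stand in part. The cause is the absent participant term, and the permutation scheme alone is not a fault. But the section does fix the test, the permutation scheme, the number of permutations and the significance level. An analyst who follows it literally would run the one-way test, which also departs from the repeated-measures principle of section 6.6, Statistical Analysis.

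A reader might infer three stronger things that the documents do not support:

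- That the test can detect almost nothing. At 2.0 log units the one-way test reached 0.36 to 0.69 in simulation A and 0.97 to 0.99 in B. Near-zero power needs a small to moderate shift together with a substantial participant share, and the protocol states neither.
- That the pairing is lost for the whole microbiota outcome. The paired pre/post distance uses it, and fold changes by quantitative PCR and diversity indices are planned as well. The paired distance measures how far a person's community moved, not whether people moved in a common direction, so it does not fully replace a PERMANOVA that respects the pairing.
- That false claims of benefit become more likely. For a treatment comparison the error runs the other way.

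**Conclusion.** The point holds in a limited form. Followed literally, the PERMANOVA ignores the crossover pairing, is conservative, and loses much power for small to moderate treatment shifts; for very large shifts the loss can be small. The size rests on an assumed participant share, an assumed shift and simulated communities, and on reading the groups as treatments; the direction follows from the variance algebra. The primary outcome, the only power calculation and the other microbiota measures are not affected. Severity is moderate: worth correcting before the analysis, but not a condition for the trial to proceed.

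**What to change.** In Protocol section 6.6.3 (c), say that the groups are treatments (if so) and which samples enter the test. Then state one of the following; either suffices:

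- PERMANOVA on Bray Curtis distances includes treatment and period as fixed factors and participant as a random (blocking) factor; or
- permutations are restricted within participant.

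If the analysis plan already contains this, align the protocol sentence with it. The cost is one sentence and a changed model specification. No new data, visits or samples are needed.
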